## 4.2 Intervention

#### 4.2.1 Standard of Care

Patients randomized to Arm 1 will undergo appropriate therapy as determined by their oncologist. These patients will either continue their current therapy or be transitioned to a new standard of care therapy at the discretion of the treating oncologist. If randomized to Arm 1, these patients may undergo palliative RT for progressive, painful lesions (a skeletal related event) at time of symptom development (not upfront palliative RT).

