## 4.2.2 Upfront, Early RT

Patients enrolled on Arm 2 of the study will undergo selective RT to 5 or less high risk bone metastases defined as 1. bulkiest sites of osseous disease ≥ 2cm, 2. disease involving the hip (acetabulum, femoral head, femoral neck), shoulder (acromion, glenoid, humeral head), or sacroiliac joints 3. disease in long bones with1/3-2/3 cortical thickness (humerus, radius, ulna, clavicle, femur, tibia, fibula, metacarpus, phalanges) 4. disease in junctional spine (C7-T1, T12-L1, L5-S1) and/or disease with posterior element involvement. Bone metastases that are within 3cm of each other will be treated as one site. Patients may undergo systemic therapy concurrently with RT at the discretion of

Page **10** of **30** Version: 2/26/16

treating radiation oncologist and medical oncologist. After completion of RT, patients will continue standard of care therapy per the treating oncologist.

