# 6.2 Subject Exclusion Criteria

- Previous radiotherapy to the intended treatment site that precludes developing a treatment plan that respects normal tissue tolerances.
- Serious medical co-morbidities precluding radiotherapy.
- Pregnant or lactating women.
- Target lesion(s) is/are complicated bone metastases that include clinical or radiological evidence of spinal cord compression or impending pathological fracture.
- Leptomeningeal disease.
- Malignant pleural effusion.
- Absolute neutrophil count (ANC) <1.0 K/mcL and platelet count <50 K/mcL at time of enrollment.
- Patients whose entry to the trial will cause unacceptable clinical delays in their planned management.

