# 12.0 CRITERIA FOR THERAPEUTIC RESPONSE/OUTCOME ASSESSMENT

#### 12.1 Primary Outcome Measurement

The primary endpoint of this study is the number of skeletal related events (SREs), which will be defined as pathological fractures, spinal cord compression, or palliative radiotherapy and orthopedic surgery to bone.

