## 14.0 BIOSTATISTICS

The primary objective of this study is to compare the rate of skeletal related events (SRE) from the date of randomization to death or 12 months, whichever occurs first, between patients who received standard of care versus upfront, early palliative RT to high-risk bone metastases. We expect 60-80% of the enrolled patients can be followed for 1 year. An SRE is defined as pathological fractures, spinal cord compression, or palliative radiotherapy and orthopedic surgery for bone pain. Data suggest that the event rate is around 60% in the standard of care arm . In our institutional experience, 75% of inpatient radiation consultation led to palliative radiation for painful bone

metastasis, an SRE. Furthermore, 61% of these lesions were diagnosed at least 4 months prior to undergoing RT. We believe 60% estimated event rate at 1-year is a conservative estimate.

The primary endpoint is a binary variable and the rate refers to proportion and is defined as the number of lesions that had SRE divided by the total number of target lesions. This analysis is lesion-based so an SRE (or no SRE) at one site does not affect the status of other sites from the same patient. We estimate that the investigational arm has the event rate around 30%. Radiation therapy is extremely effective in alleviating pain due to bone metastases with 70-80% pain control. By preventing the development of significant bone pain, which often leads to SREs, RT can effectively reduce SREs, To this end we will analyze at least 66 patients with valid SRE endpoint (randomized 1:1 to each arm) to achieve >80% power in detecting such a difference using a two-sample, one-sided proportion test with alpha<0.05. Since patients who withdraw before the endpoint can be evaluated will not be included in the analysis (i.e., it will NOT be an intent-to-treat analysis) we will over-accrue to account for withdrawals to ensure a minimum of 33 patients in each arm (subject to stratification, see Section 15.2) who can contribute the analyzable endpoint of SRE. We believe an additional 10% would be sufficient so totally we expect to randomize 74 patients. A small portion of patients (<15%) may have multiple lesions, in which case they will be treated as independent analysis units. In other words, the eventual effect sample size may be slightly higher than 66 because this objective will be analyzed per lesion.

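### Palliative RT to bone is both the Arm 2 treatment and a component of the primary SRE endpoint, and no planned analysis separates it from fracture, cord compression and surgery

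*Combined protocol and SAP*

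**What the plan says.** Section 12.1 defines the primary endpoint as the number of SREs, counting fracture, cord compression and "palliative radiotherapy and orthopedic surgery to bone". Section 1.0 joins RT and surgery with *or*; Sections 2.0, 12.1 and 14.0 use *and*. Section 4.2.1 shows that RT counts on its own, since it says of Arm 1 that "these patients may undergo palliative RT for progressive, painful lesions (a skeletal related event) at time of symptom development (not upfront palliative RT".

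Under Section 4.2.2, Arm 2 patients "will undergo selective RT to 5 or less high risk bone metastases". Section 14.0 analyses the endpoint as a binary result per target lesion, from randomization to death or 12 months, and treats lesions as unaffected by events at other sites. On the control rate it says: "Data suggest that the event rate is around 60% in the standard of care arm". It assumes about 30% in Arm 2.

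Three further points bear on this:
- No sentence states that protocol RT is outside the SRE count, or how repeat RT to an irradiated lesion is scored.
- Section 14.0 plans no comparison by component and none without RT. The secondary endpoints are SRE-related hospitalization, BPI, EQ-5D-5L, pain-free survival, overall survival and toxicity.
- Section 13.0 ends protocol participation at 12 months or at an SRE.

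**The concern.** A composite is hardest to interpret when one component is the experimental treatment itself, given at a different time. A target lesion that becomes painful and is irradiated in Arm 1 scores an event. A similar lesion irradiated early in Arm 2 does not, and scores for RT only if it is irradiated again.

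Repeat RT may be less likely for reasons other than bone health. Section 6.2 recognises that earlier RT can limit later RT, by excluding patients with "Previous radiotherapy to the intended treatment site that precludes developing a treatment plan that respects normal tissue tolerances". Physicians are told the allocation (Section 15.2), and giving palliative RT is their decision. Follow-up imaging is discretionary (Section 10.0). No independent review of SREs is described.

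At stake is what a positive result means. The hypothesis names fracture and cord compression alongside RT and surgery. A lower composite rate in Arm 2 could come from fewer of those complications, from less painful progression needing RT, or partly from a lower tendency to irradiate a lesion twice. The planned primary analysis cannot tell these apart. The secondary endpoints do not isolate fracture, cord compression or surgery, and the hospitalization endpoint is itself tied to SREs.

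**Working it through.** **Inputs from Section 14.0.** Control rate 60%; Arm 2 rate 30%; one-sided alpha 0.05; two-sample proportion test; 33 analysable per arm; 10% over-accrual.

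**Input not in the documents.** s, the share of control SRE lesions whose only event is palliative RT. It is assumed here to range from 30% to 80%. The fraction of those RT events avoided in Arm 2, e, is also an assumption.

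**Step 1: reproduce the design.** The pooled z-test without continuity correction needs 33 per arm for 80% power. At 33 per arm:
- SE under the null = √(2 × 0.45 × 0.55 / 33) = 0.1225
- SE under the alternative = √((0.24 + 0.21) / 33) = 0.1168
- Power = Φ((0.30 − 1.645 × 0.1225) / 0.1168) = 80.1%
- 66 / 0.90 = 73.3, rounded up to 74 randomized

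The plan's 66 and 74 both reproduce. The sample size is not the problem.

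**Step 2: hold fracture, cord compression and surgery equal in the two arms.** The rate of these hard events is then 0.60 × (1 − s) in both arms, and

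Arm 2 rate = 0.60 × (1 − s × e).

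Setting this to 0.30 gives s × e = 0.50. Since e cannot exceed 1, the full planned effect needs s of at least 50%.

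**Step 3: results** (control 60%, 33 per arm, one-sided 0.05):

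| s | Hard events, each arm | e | Arm 2 rate | Power |
|---|---|---|---|---|
| 30% | 42% | 50% | 51% | 18% |
| 30% | 42% | 100% | 42% | 43% |
| 40% | 36% | 100% | 36% | 62% |
| 50% | 30% | 50% | 45% | 33% |
| 50% | 30% | 100% | 30% | 80% |
| 67% | 20% | 75% | 30% | 80% |
| 75% | 15% | 70% | 28.5% | 84% |
| 75% | 15% | 80% | 24% | 92% |

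In the 67% / 75% row, Arm 1 has 40% RT-only plus 20% hard events, and Arm 2 has 10% plus 20%.

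**Step 4: a smaller observed difference can also be significant.** For 20/33 v 13/33 (61% v 39%), z = 0.212 / √(2 × 0.25 / 33) = 1.72, above 1.645.

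**Step 5: power of an RT-free comparison.** If hard events were halved from 30% to 15% at 33 per arm, power = Φ((0.15 − 1.645 × 0.1028) / 0.1011) = 42.5%.

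**Step 6: can the RT-free comparison be run on the planned data?** Not reliably. Section 13.0 ends participation at an SRE, so an RT event in Arm 1 can stop observation of a later fracture or compression. That would undercount hard events in Arm 1 and bias an RT-free comparison against Arm 2. It also conflicts with Section 14.0, where an event at one site is meant to leave the other sites' status unaffected.

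The calculation treats lesions as independent. It also ignores Arm 2 lesions that avoid RT but fracture later.

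**The case against.** The strongest defence is that the composite is an established one and RT belongs in it. The background in Section 3.0 lists radiation to bone among SREs. It justifies the endpoint by quality of life, measurability and use in earlier trials, not by fracture, compression and surgery alone. By Section 4.2.1 an Arm 1 RT event follows painful progression, and avoiding that is a real benefit. This stands, and it is why the composite need not be replaced. A reader might infer that a positive result would show only that RT was moved earlier. The documents do not support that. BPI, EQ-5D-5L and pain-free survival do not count RT as an event, so they give a partial check on symptoms.

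A reader might also infer that every Arm 2 target lesion has an SRE on the day protocol RT begins. That reading is strained. Section 4.2.1 sets upfront RT apart from the RT event, Section 14.0 refers to treatment for bone pain, protocol RT goes to lesions with no or minimal symptoms, and the 30% assumption makes sense only if protocol RT is not counted. What remains is that the definition should say so.

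Nor does Section 14.0 rest its 60% mainly on palliative RT. It cites published data first and then uses institutional experience to call 60% conservative. Its statement that "75% of inpatient radiation consultation led to palliative radiation for painful bone" metastasis describes consultations, not the RT share of SREs. Section 3.0 gives two-thirds for a similar quantity. Neither figure estimates s.

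Finally, reaching the full effect at s = 50% requires that no target lesion is re-irradiated in 12 months. Section 6.2 excludes only prior RT that rules out a tolerable plan, so re-irradiation is otherwise possible. That case is a boundary, not an expectation.

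**Conclusion.** The concern holds as a limit on interpretation. Palliative RT is the treatment in one arm and an outcome in both, and nothing planned separates it from the other components. With no hard event prevented, the full 60% v 30% effect arises when s × e = 0.50, which requires s of at least 50%. Below that, a significant result is still possible, but its probability depends strongly on the assumptions: 62% at s = 40%, e = 100%, and 18% at s = 30%, e = 50%.

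All of this rests on an assumed s and e, equal hard-event rates in the two arms and independent lesions. It shows what the design permits, not what is likely. It does not fault the sample size or argue against the composite as the primary endpoint. Should-fix, at low cost.

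**What to change.** - **Endpoint definition (Sections 12.1 and 14.0).** State that protocol RT to an Arm 2 target lesion is not an SRE, and that later palliative re-irradiation of it is. Use the same wording for RT and surgery throughout.
- **Analysis (Section 14.0).** Keep the composite as primary. Pre-specify a table of each SRE component by arm, and a supportive analysis of fracture, cord compression or orthopaedic surgery without RT, with a confidence interval.
- **Follow-up (Section 13.0).** Let outcome data collection continue to 12 months or death after an SRE. The lesion-based primary analysis needs this in any case.
- **Conclusion.** Limit claims to the composite unless the RT-free estimate and its interval support a statement about hard skeletal events. Agreement in direction alone is too weak, since with no hard-event effect it would occur nearly half the time by chance.

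The cost is protocol wording, one component table, one supportive analysis and some added data collection after an SRE. The sample size does not change. The supportive analysis will have low power (about 43% for 30% v 15% at 33 per arm) and should be labelled so.

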# 12.2 Secondary Outcome Measurements

Patients on both arms will be followed for accumulation of surrogates of health care cost, including number and duration of hospitalizations for SREs.

All study participants will be assessed for health related quality of life, measured using the BPI questionnaires, and health utilities using the EQ-5D-5L form.

Patients enrolled on both arms of the study will also be included in an analysis of pain-free survival, defined as time from study entry to start of opioids or death. Patients enrolled on both arms of the study will also be included in an analysis of overall survival, defined as time from study entry to death.

#### 13.0 CRITERIA FOR REMOVAL FROM STUDY

Patients will be removed from the study if any of the following criteria are met, after review by the principal investigator:

- 1. A change in the patient's medical status unrelated to RT results in the patient being unable to comply with the protocol.
- 2. Patient is unable to continue follow-up as outlined within the protocol
- 3. Patient is found to be ineligible based on the criteria in section 6.0 of this protocol.
- 4. Patient requests to withdraw from the protocol.
- 5. Patient death.

Otherwise, patients will continue on protocol until 12 months have elapsed since date of randomization or until an SRE occurs.

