Palliative radiation therapy is a well-established, frequently used treatment for patients with metastatic disease. It is often the standard of care for patients with symptomatic metastatic lesion. It is extremely unlikely to be more toxic or cause earlier deaths.

We expect to enroll all 74 patients within 2 years.

Secondary objectives will be analyzed per patient. Unless otherwise specified, all endpoints are defined within the time window from the date of randomization to death or 12 months, whichever occurs first.

To compare the number of hospitalizations related to SREs between standard of care and upfront, early palliative RT arms we will employ a Wilcoxon rank sum test.

To compare quality of life between standard of care and RT arms, using the Brief Pain Inventory (BPI) and EuroQol Group EQ-5D-5L forms, we will test the difference (between the two arms) of the survey results at the following time points: 3 months, 6 months, 12 months and optionally but recommended within one week of any SRE. The individual quantitative scores derived from the BPI, and the utility scores as well as the overall health scores derived from EQ-5D-5L, will be summarized at these assessment times using descriptive statistics (means and standard deviations, medians and quartiles). Differences between the two arms in terms of these quantitative scores at various time points of interest will be evaluated for both statistical and clinical significance using Wilcoxon rank

Page **22** of **30** Version: 2/26/16

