sum tests and established minimally important differences (MIDs) for the various measures, respectively. For scale scores with no established MIDs, the "half standard deviation" rule will be applied (i.e., differences of a half standard deviation will be considered clinically significant). At the conclusion of the study data at each time point will be presented, the number of patients in each group at a given time point will be documented, and the mean EQ-5D-5L and BPI scores for each group will be plotted over time and longitudinal pattern will be examined with the possibility of proposing more complicated regression methods such as the linear mixed models. The categorical answers (e.g., YES vs NO) from EQ-5D-5L will be compared between the two arms using Fisher"s test at each time point as well and odds ratios together with confidence intervals will be computed. Other non-quantifiable answers (e.g., treatment receiving for pain) will be summarized descriptively. For the last question in BPI, the score for pain interference on the BPI Short Form is the mean of the 7 interference questions as long as at least 4 are completed.

For comparing pain-free survival and overall survival between the two arms, both of which are time to event endpoint (time from randomization to start of opioids or death which is not necessarily within 12 months from randomization), we will use log-rank test.

To evaluate CTCAE v4 toxicity events in the upfront RT arms, we will tabulate all toxicities and summarize the CTCAE v4.03 scores and present descriptive statistics. This will be done at 3 months, 6 months, and 12 months from randomization.

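### Overall and pain-free survival run past 12 months, but the plan provides no collection of deaths or opioid starts after removal, an SRE or month 12, and no censoring rule

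*Combined protocol and SAP*

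**What the plan says.** Section 13 lists the grounds for removal, each subject to review by the principal investigator. Criterion 1 applies when a change in medical status "unrelated to RT results in the patient being unable to comply with the protocol". Criterion 2 reads "Patient is unable to continue follow-up as outlined within the protocol" and carries no condition on cause. The section closes: "Otherwise, patients will continue on protocol until 12 months have elapsed since date of randomization or until an SRE occurs".

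Section 10 and its assessment table schedule visits at 3, 6 and 12 months, plus optional assessments around an SRE. No later contact is scheduled.

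Section 12.2 includes patients from both arms in the analysis of "overall survival, defined as time from study entry to death" and defines pain-free survival in the same way, with opioid start or death as the event. Section 14 sets a default window ending at death or 12 months, then departs from it for these two endpoints: "time from randomization to start of opioids or death which is not necessarily within 12 months from randomization". Both are compared by log-rank test. No censoring rule, event target or power is stated for either.

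**The concern.** The two survival endpoints need dates of death and first opioid for every randomised patient, including dates after the patient has left the study. Sections 10 and 13 describe when patients leave, and no section says how those dates are obtained afterwards. An analyst working from the text could reasonably censor at removal, at the SRE or at 12 months. These choices have different consequences. A patient too ill to comply is at raised risk of death, so censoring at that moment breaks the independent-censoring assumption behind Kaplan-Meier and the log-rank test. An SRE is the event the intervention is meant to prevent, so stopping there cuts follow-up at different rates in the two arms.

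Scheduled adverse-event evaluation excludes Arm 1 (Section 10). Survival is therefore the main between-arm check on the statement in Section 14 about palliative RT that "It is extremely unlikely to be more toxic or cause earlier deaths".

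**Working it through.** **1. The plan's own figures.** None is given for survival. The primary sample size reproduces: per arm, n = [1.645·√(2×0.45×0.55) + 0.842·√(0.60×0.40 + 0.30×0.70)]² / 0.30² = 32.95, so 33, with power 0.8006. Then 66/0.90 = 73.3, so 74 randomised, or 37 per arm.

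**2. What the text provides after each exit.**

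| Exit | Source | Deaths or opioid starts collected afterwards? | Censoring rule? |
|---|---|---|---|
| Too ill to comply, or cannot continue follow-up | Section 13 | Not stated | Not stated |
| SRE | Section 13 | Not stated beyond optional assessments within one week | Not stated |
| 12 months | Sections 10 and 13 | Not stated | Not stated |

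**3. Within-arm effect if survival is censored at removal.** Assumptions, not in the documents: exponential survival; a fraction q of patients who would die is removed one month before death. As an approximation, apparent mortality = 1 − exp[−(1−q)·H], with H = −ln(true 12-month survival). The simulated column used 400,000 patients per scenario.

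| True 12-month mortality | H | q | Approximation | Simulated |
|---|---|---|---|---|
| 40% | 0.511 | 0.25 | 31.8% | 32.1% |
| 40% | 0.511 | 0.50 | 22.5% | 23.0% |
| 20% | 0.223 | 0.25 | 15.4% | 15.5% |
| 20% | 0.223 | 0.50 | 10.6% | 10.6% |

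**4. Between-arm effect on overall survival when the arms truly do not differ.** This was a simulation with 37 per arm, 4,000 runs and a two-sided 0.05 log-rank test.

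- Death and SRE share a gamma frailty with variance 1 (assumed). A 12-month event probability p then needs a baseline hazard of [1/(1−p) − 1]/12 per month.
- 12-month survival is set at 60% or 80%. This is borrowed from the 60-80% that Section 14 expects to follow for a year; the documents give no survival figure for this population. Hazards: 0.667/12 = 0.056 and 0.25/12 = 0.021.
- SRE by 12 months is 60% (standard) and 30% (RT), from Section 14. Hazards: 1.5/12 = 0.125 and 0.429/12 = 0.036. Section 14 states these rates per lesion; applying them per patient is an assumption.
- Removal for decline: 40% of patients in each arm, at 60-100% of their survival time (assumed), with a 12-month cut.

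| Where survival stops | Deaths (60% / 80% survival) | Mean HR, RT v standard | Type I error |
|---|---|---|---|
| 36 months, everyone followed | 49.4 / 31.7 | 0.99 / 1.00 | 0.051 / 0.051 |
| 12 months | 29.6 / 14.8 | 1.01 / 1.00 | 0.048 / 0.051 |
| Removal for decline, equal in both arms, or 12 months | 17.8 / 8.9 | 1.00 / 0.99 | 0.049 / 0.052 |
| First SRE or 12 months | 19.7 / 8.9 | 1.23 / 1.27 | 0.067 / 0.057 |

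The death counts agree with direct arithmetic. At 12 months, 74×0.40 = 29.6 and 74×0.20 = 14.8. With 40% removed, 29.6×0.60 = 17.8 and 14.8×0.60 = 8.9. At 36 months, survival is 1/(1 + 36×0.667/12) = 0.333 and 1/(1 + 36×0.25/12) = 0.571, giving 74×0.667 = 49 and 74×0.429 = 32 deaths.

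**5. Reading the SRE row.** Stopping at an SRE removes frail patients faster from the standard arm, so those left at risk there look healthier. Rejections fall mainly against RT: 0.059 v 0.008 at 60% survival. With 1,000 per arm the HR is still 1.22, so this is not a small-sample effect. It is modest beside sampling error: the standard error of log HR is roughly 2/√19.7 = 0.45, against ln(1.23) = 0.21.

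**The case against.** The strongest reply is that the plan never says survival is censored on leaving. Section 12.2 includes patients from both arms in both analyses. Section 14 extends the endpoints past 12 months, which presupposes later data. Section 11.1 brings events leading to death from progression into the safety and efficacy analyses. The lesion-based primary analysis in Section 14 also sits oddly with a stop at the first SRE, so Section 13 may not have been meant to end all data collection. Section 10 lets a telephone contact replace a missed visit, which should keep the number removed down. All of this stands as evidence of intent. It supplies neither a collection procedure nor a censoring rule, and the telephone provision does not say it covers patients already removed.

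A reader might infer more: that survival is informatively censored by a rule that differs by arm, because criterion 1 is limited to changes unrelated to RT and Arm 1 has no upfront RT. The documents do not support that.

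- Criterion 2 removes anyone unable to continue follow-up, whatever the cause, so a patient who declines because of RT can leave as well.
- Nothing says how often decline would be judged RT-related, so any hazard ratio for this route mostly reflects the removal fractions assumed. Removal half as frequent in the RT arm gives about 1.3; removal 10% less frequent gives about 1.07.
- The 12-month stop is fixed and the same in both arms, so it is neither informative nor arm-dependent.
- The 60-80% one-year follow-up figure gives no reasons, and the shortfall may be deaths, which are events.

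**Conclusion.** The point holds as an omission and an internal mismatch. The survival endpoints reach beyond the period for which the plan describes any follow-up, and censoring is undefined. The consequence is conditional on survival being censored when patients leave:

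- Removal for deterioration would overstate survival in each arm, by an amount set by how many dying patients are removed first. If removal is equal between arms, the null comparison is not biased.
- Stopping at an SRE is the clearer arm-dependent route, with an illustrative null HR of 1.23 to 1.27 against RT and type I error of 0.057 to 0.067. This needs SRE and death to share risk. If they were independent within each arm, the bias would vanish.
- The 12-month stop contradicts Section 14 and costs events (about 30 rather than 49 deaths, or 15 rather than 32, against an assumed 36-month follow-up), without bias.

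The simulations cover overall survival only; pain-free survival has the same gap but was not modelled. Both are secondary endpoints with no stated power, so this should be corrected but does not affect the primary comparison.

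**What to change.** State in Sections 13 and 14 that removal, an SRE or reaching 12 months ends study visits and questionnaires only as Section 13 provides, and does not end survival follow-up. For every randomised patient in both arms, unless consent for record review is withdrawn, collect date of death and date of first opioid from the medical record or by telephone up to one stated data cut-off. Censor overall survival at the last date known alive, and pain-free survival at the last date known alive and opioid-free, by that cut-off.

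Alternatively, restrict both endpoints to 12 months and require complete ascertainment to that point in all randomised patients, including those removed and those with an SRE. This is simpler but gives up the later events.

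Criterion 1 can keep its wording. Once survival is collected after removal, its limitation to changes unrelated to RT no longer affects these endpoints. Deleting it could end toxicity visits for patients who decline because of RT, and toxicity in the RT arm is a stated objective.

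The cost is protocol wording and some coordinator time for record review in at most 74 patients. No visits or procedures are added.
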